8.1.2. Imputation of Partial Dates

Imputed dates will not be used to derive study day, duration (eg, duration of adverse events), or elapsed time variables. Imputed dates will be displayed in listings and identified as imputed.

Partial date imputation will follow Analysis Data Model (AdAM) conventions. The AdAM approach is to populate the numeric date variables with the imputed date and add a flag variable to the dataset that indicates the level of imputation.

The flag variable can contain the values: blank, ‘D’, ‘M’, ‘Y’.

Blank indicates that no imputation was done

D = ‘Day’ indicates that the day portion of the date is imputed

M = ‘Month’ indicates that the month and day portions of the date are imputed

Y = ‘Year’ indicates that the entire date (year, month, and day) is imputed

8.1.3. Adverse Events

Imputations in the adverse events dataset are used for slotting events to the appropriate study time periods and for sorting in data listings. They will not be used to calculate duration of adverse events (AEs). If an AE start or end date is missing, then the duration of the AE will be set to missing.

As a rule, the missing start date elements will be imputed with following priorities:

- The event is counted as TEAE for IgPro20 with the earliest onset possible.
- The event is counted as TEAE for placebo with the earliest onset possible.

CONFIDENTIAL

For subjects randomized to Placebo in the Double-blind Treatment Period who have already transitioned to the Open-label Treatment Period, if due to missing elements the event qualifies to either IgPro20 or placebo, the event is assigned to be treatment-emergent in the IgPro20 Open-label Treatment Period.

Table 2: Imputation of Missing Dates for AEs

Date	Missing Element	Rule
Start Date	day, month, and year	
Do not impute completely missing AE start dates.
 
Double-blind Treatment Period
 
 The AE will be deemed treatment-emergent during the Double-blind Treatment Period (Week 1-25) if the AE end date does not indicate that the AE ended prior to IMP start date (Week 1), otherwise, the AE will be deemed not treatment emergent. 
Open-label Treatment Period
 
 The AE will be deemed treatment-emergent during the Open-label Treatment Period (Week 25-53) if the AE end date does not indicate that the AE ended prior to IMP start date (Week 25), else the AE will be deemed treatment-emergent in the Double-blind Treatment Period (Week 1-25) if the AE end date does not indicate that the AE ended prior to IMP start date (Week 1), otherwise, the AE will be deemed not treatment emergent.
Start Date	day, month only	
Double-blind Treatment Period
 
 If the year of AE start date is the same as the year of IMP start date (Week 1), and the AE end date indicates the AE ended after IMP start date (Week 1), then set AE start date to IMP start date (Week 1), otherwise set AE month and day to January 1st 
Open-label Treatment Period
 
 If the year of AE start date is the same as the year of IMP start date (Week 25), and the AE end date indicates the AE ended after IMP start date (Week 25), and IMP start date (Week 25) is not missing then set AE start date to IMP start date (Week 25), else if the year of AE start date is the same as the year of IMP start date (Week 1), and the AE end date indicates the AE ended after IMP start date (Week 1) then set AE start date to IMP start date (Week 1), otherwise set AE month and day to January 1st
	day only	
Double-blind Treatment Period
 
 If the month/year of AE start date is the same as the month/year of IMP start date (Week 1), and the AE end date indicates the AE ended after IMP start date (Week 1) then set AE start date to IMP start date (Week 1), otherwise set day of AE start date to 1 
Open-label Treatment Period
 
 If the month/year of AE start date is the same as the month/year of IMP start date (Week 25), and the AE end date indicates the AE ended after IMP start date (Week 25), and IMP start date

CONFIDENTIAL

Date	Missing Element	Rule
		(Week 25) is not missing then set AE start date to IMP start date (Week 25), 
else if the month/year of AE start date is the same as the month/year of IMP start date (Week 1), and the AE end date indicates the AE ended after IMP start date (Week 1) then set AE start date to IMP start date (Week 1),
End Date	any date element	No imputation for completely or partially missing AE end dates; as applicable, report the AE as ongoing and the AE duration as missing.

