8.3.1. Study Time Periods for Adverse Events

Adverse events (AEs) with onset date/ time after start of first infusion of IMP are TEAEs. Assessment whether an AE is considered treatment-emergent, will take place after imputation of partially missing dates (see Section 8.1.2).

The TEAE analysis will be done for both treatment periods. An AE will be counted for the analysis of a period if the onset of the event falls within the period. For the definition of start and end of the periods see Table 9.

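### SAP Table 2 dates some ongoing adverse events before first dose when only the month or year of onset is known, so they lose TEAE status

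*SAP*

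**What the plan says.** SAP Section 8.1.3 gives AE date imputation a working role: "Imputations in the adverse events dataset are used for slotting events to the appropriate study time periods". It then sets two priorities for missing start-date elements. First, "The event is counted as TEAE for IgPro20 with the earliest onset possible"; second, "The event is counted as TEAE for placebo with the earliest onset possible". For placebo-randomized subjects who have moved to open-label treatment, an event that could belong to either product goes to open-label IgPro20.

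Table 2 applies this in rows:

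- **Start date wholly missing.** Nothing is imputed. The event is treatment-emergent in the double-blind period "if the AE end date does not indicate that the AE ended prior to IMP start date (Week 1").
- **Start date partial, same year or same month/year as first dose.** The event must pass a different test: "and the AE end date indicates the AE ended after IMP start date (Week 1), then set AE start date to IMP start date". If it fails with only the day missing, "otherwise set day of AE start date to 1". If it fails with day and month missing, onset becomes 1 January of the reported year.
- **End date.** "No imputation for completely or partially missing AE end dates; as applicable, report the AE as ongoing".

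Section 8.3.1 fixes the order of steps: "Assessment whether an AE is considered treatment-emergent, will take place after imputation of partially missing dates". Sections 8.3.1 and 11.2 both require onset after the start of the first infusion.

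**The concern.** The two start-date tests look like the same idea but handle an absent end date in opposite ways. The wholly-missing row asks whether the end date rules the event out, and an ongoing event passes. The partial rows ask whether the end date rules the event in, and an ongoing event has nothing to show. Learning the month or year of onset can therefore turn a TEAE into a non-TEAE.

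The events exposed are those without a usable end date, chiefly unresolved ones. TEAE frequencies are the protocol's secondary safety endpoint. After termination, SAP Sections 11.4 and 11.5 send laboratory, vital-sign, ECG and physical-examination data to SDTM datasets only, so the TEAE tables are the main summarized safety output. A misclassified event leaves all of those tables and, if serious, the separate listing of serious TEAEs.

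**Working it through.** The plan states no figure here. The check applies Table 2 literally.

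**Worked example.** Assume first dose on 17 September 2024.

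| Start date recorded | Event ended 5 October 2024 | Event ongoing |
|---|---|---|
| September 2024, day missing | 17 September 2024 | 1 September 2024, before dose, not a TEAE |
| 2024, day and month missing | 17 September 2024 | 1 January 2024, before dose, not a TEAE |
| Wholly missing | TEAE | TEAE |

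The 1 January date is also implausible on the protocol's own terms. AE observation begins at consent (protocol 10.2.4) and screening starts at Day -28, here 20 August 2024.

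**How often the fallback lands before dose.** Assume ongoing events, every first-dose date in 2024 equally likely, and true onset uniform over days 0 to 167 after first dose. That gives 366 × 168 = 61,488 combinations.

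*Day missing.* In a month of n days, n(n+1)/2 combinations have onset in the first-dose month. Of these, n have first dose on the 1st and are not backdated, which leaves n(n-1)/2 that are. For seven months of 31 days, four of 30 and one of 29:

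- onset in the first-dose month: 7×496 + 4×465 + 435 = 5,767
- imputed before dose: 7×465 + 4×435 + 406 = 5,401
- 5,401/5,767 = 93.7% of events starting in the first-dose month
- 5,401/61,488 = 8.8% of events over the whole 24 weeks

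*Day and month missing.*

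- onset in the first-dose year: 199×168 + 167×168/2 = 47,460
- not backdated (first dose on 1 January): 168
- (47,460 - 168)/47,460 = 99.6% of events starting in the first-dose year
- 47,292/61,488 = 76.9% over the whole 24 weeks

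For events with an end date after first dose, the share is 0%. If the wholly-missing condition replaces the partial-date condition, the share for ongoing events is also 0%, and the example events move to 17 September 2024.

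**Effect of one event on incidence.** SAP Section 3 gives 16 randomized subjects. At 2:1, 16 × 2/3 = 10.7 and 16 × 1/3 = 5.3, so about 11 and 5. Then 1/11 = 9% and 1/5 = 20%. Both assume that the lost event is the subject's only TEAE.

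**Open-label rows.**

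- The day-only row has no fallback branch. With Week 1 on 17 September 2024 and Week 25 on 4 March 2025, an ongoing event dated March 2025 receives no imputed date from that row.
- The day-and-month row sends an ongoing event to 1 January. With Week 1 on 12 March 2024 and Week 25 on 27 August 2024, an event dated 2024 goes to 1 January 2024, before first dose.

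**The case against.** The strongest reply is that Section 8.1.3 states its intent and that intent favours counting the event. A programmer who follows the priority list could treat an ongoing event as not having ended before dose. That reading is possible, but Table 2 does not say it, and the contrast with the wholly-missing row makes it hard to read into the partial rows.

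Other parts of the reply stand:

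- A reader might infer that ongoing events in general drop out. They do not. Ongoing events with a full start date, a wholly missing start date, or a partial start in a later month or year remain TEAEs. A partial end date in a later month can still show that the event ended after first dose.
- A reader might infer that TEAEs are in fact undercounted in both arms. The documents give no count of partial dates. Sites ask about AEs at every visit (protocol 10.2.6.1), and visits at Weeks 1, 2 and 5 limit uncertainty about onset near first dose.
- Affected events stay visible. All AEs are listed, imputed dates are flagged (SAP 8.1.2), and every analysis is descriptive.
- A reader might infer that the open-label rows certainly move events of IgPro20-randomized subjects to Week 25. Table 2 does not say which subjects those rows cover, and the text of Section 8.1.3 gives open-label priority only to placebo-randomized subjects who transitioned. The shift would also need an end date after Week 25, so it would not touch ongoing events.

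**Conclusion.** The rule is wrong as written, within a narrow scope: a partial start date in the first-dose month (day missing) or first-dose year (day and month missing), with no end date showing that the event ended after first dose. Unless first dose fell on the imputed date itself, such an event is classed as pre-dose, against the section's stated priority and its own wholly-missing row.

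The practical effect is conditional and probably small with 16 subjects. The 93.7% and 99.6% figures are shares of affected-type events under assumed uniform dates, not estimates of how many TEAEs this study loses. The 9- and 20-point shifts rest on the assumed 11:5 split and on a subject having no other TEAE.

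The open-label rows need clarifying rather than condemning. Read literally, without the limit in the text, they could move an IgPro20-randomized subject's ambiguous event out of the double-blind period. That is the only period SAP Sections 5 and 11 summarize, although Section 8.3.1 still mentions TEAE analysis for both.

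**What to change.** 1. In every partial-date row of Table 2, replace the end-date condition with the one in the wholly-missing row ("if the AE end date does not indicate that the AE ended prior to IMP start date (Week 1"), using the Week 25 equivalent where relevant. State that missing and ongoing end dates satisfy it.
2. Change the TEAE definition in SAP Sections 8.3.1 and 11.2 from onset after the start of IMP to the protocol's at-or-after (protocol 9.4.7). Otherwise an onset set to the first-dose date may still fail.
3. Add the missing fallback branch to the open-label day-only row.
4. State that Week 25 priority applies only to placebo-randomized subjects who transitioned, as the text of Section 8.1.3 says.

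The cost is a wording change and a small change to the derivation code. Some screening events that were still ongoing at first dose and have partial start dates would now count as TEAEs. That is the conservative direction the SAP already chose. If outputs exist, check the AE data for affected records and rerun only if any are found.

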8.1.4. Medical History

Missing dates for medical history will not be imputed.

8.1.5. Initial Diagnosis of Post-COVID POTS

Table 3: Imputation of Missing Dates for Diagnosis of Post-COVID POTS

Missing Element	Rule
day, month, and year	No imputation for completely missing dates. Time since first diagnosis will be set to missing.
Day, month only	Set the date to January 1 st .
day only	Set the date to 1.

8.1.6. Concomitant Medication

Impute start dates for use to derive the reference variables for concomitant medication (CM) start relative to treatment; include any imputed dates in analysis datasets with an identifier as imputed. The reference variables will be used to differentiate before, during and after treatment for the concomitant medication.

As a rule, the missing start date elements will be imputed with following priorities:

1. The medication is 'concomitant' to IMP
2. The medication is 'prior' to IMP

Table 4: Imputation of Missing Dates for Concomitant Medication

Date	Missing Element	Rule
Start Date	day, month, and year	Completely missing medication start dates will not be imputed and all values that depend on this date will be set to missing. The medication will be considered 'concomitant'.
End Date	day, month, and year	Medication is considered ongoing at the end of the study.
	Day, month only	
• If the year of concomitant medication (CM) start date is the same as the year of IMP start date (Week 1), and the CM end date indicates the CM ended after IMP start date (Week 1) then set CM start date to IMP start date (Week 1),• otherwise set CM month and day to January 1st
	day only	
• If the month/year of CM start date is the same as the month/year of IMP start date (Week 1), and the CM end date indicates the CM ended after IMP start date (Week 1) then set CM start date to IMP start date (Week 1),• otherwise set day of CM start date to 1
	Day, month only	Set CM end month and day to December 31 st
	day only	Set day of CM end date to the last day of the month.

8.2. Derived Variables

The following sections provide a general description of the derived and transformed variables to be used in data analyses. Separate analysis dataset specifications provide full details on all data derivations and transformations.

In this study, an Electronic Clinical Outcomes Assessment (eCOA) device will be used to collect data for several outcomes.

8.2.1. Reference Dates

Reference dates are used to assign study periods relative to treatment. The reference date is the date of the start of the period (Section 8.3).

8.2.2. Heart Rate and Change in Heart Rate During Standardized Standing Test

Heart rate for standing test will be measured at the end of the 10 minutes in supine position and at 1, 3, 5, 7, and 10 minutes of standing.

The change in heart rate during the standing test is calculated as the difference of the average of the two highest heart rate measures (bpm) within 10 minutes of standing and the heart rate measure (bpm) at the end of the 10 minutes in supine position.

If in one subject the standardized standing test was repeated at a visit results of the last standing test will be used for the summarizing analysis.

8.2.3. Systolic Blood Pressure and Change in Systolic Blood Pressure During Standardized Standing Test

Blood pressure for standing test will be measured at the end of the 10 minutes in supine position and at 1, 3, 5, 7, and 10 minutes of standing.

The change in systolic blood pressure during the standing test is calculated as the difference of the minimum of all systolic blood pressures (mmHg) within 10 minutes of standing and the systolic blood pressures (mmHg) at the end of the 10 minutes in supine position.

If in one subject the standardized standing test was repeated at a visit results of the last standing test will be used for the summarizing analysis.

8.2.4. Study Day

If the date of interest occurs on or after the date of the start of first IMP infusion, then the study day will be calculated as (date of interest – date of the start of first IMP infusion) + 1. If the date of interest occurs before the date of the start of first IMP infusion, then the study day will be calculated as (date of interest – date of the start of first IMP infusion). There is no study day 0.

8.2.5. Study Week

The start of a study week is the day of the first infusion of IMP in that week as recorded in the infusion diary. Events that occur after premature discontinuation of IMP will not be assigned to a specific week.

End date of last study treatment week =
minimum of (Date of last visit, date of 1st infusion in last study week + 6 days)

The end of a study week is the day before the start of the next study week. In case of longer treatment interruptions planned weeks will be considered.

8.2.6. Baseline Definition

Baseline is defined as the most recent, non-missing value prior to the start date and time of the first IMP infusion. Results from repeat test prior to the start date and time of the first IMP infusion will be considered.

For COMPASS-31, the assessment at the Screening visit will be used as baseline value (for total as well as for all domains). Therefore, if the assessment at the Screening visit is missing, COMPASS-31 will be considered missing.

If the time of assessment is after the time of the first IMP infusion, then this assessment is NOT considered baseline.

8.2.7. Change from Baseline or Reference Visit

Change from baseline will only be calculated for measures that have post-baseline records. Change from baseline is calculated as:

change from baseline = visit value – baseline value.

If either the baseline or visit value is missing, the change from baseline is set to missing as well.

The change from reference visit will be calculated following the same rules.

8.2.8. Multiple Assessments

All data will be reported according to the nominal visit date for which it was reported (that is, no visit windows will be applied during data set creation). Unscheduled data will not be included in by-visit summaries but may contribute to the End of Study (EOS) value.

For data included in the summarizing analyses, data from all assessments (scheduled and unscheduled), including multiple assessments, will be included in listings.

8.2.9. Actual Treatment

The subject's actual treatment will be derived from exposure data delivered by IRT. If a subject receives IMP that is the same as the assigned treatment, then actual treatment is the assigned treatment. If a subject receives IMP that is different from the assigned treatment for the entire time of treatment, then actual treatment is the different treatment (the treatment actually received).

8.2.10. Body Mass Index (BMI)

BMI will be calculated using the following formula:

$$\text{BMI (kg/m}^2\text{)} = \text{Weight (kg)} / [\text{Height (m)}]^2$$

using the height measured at Screening and the weight measured at Day 1. If weight at Day 1 is not available, the assessment at Screening will be used. If neither is available, then BMI is missing.

8.2.11. Patient-Reported-Outcome Assessments

All patient-reported outcomes (PRO) measurements will be performed at the time points specified in the Schedule of Activities and recommended to be administered BEFORE any other study activities unless otherwise specified. All assessments will be administered electronically unless otherwise specified. The mode of administration can be changed for exceptional circumstances after the consultation with the Sponsor. The scoring will be performed based on the scoring manual of each instrument below.

COMPASS-31

The COMPASS-31 is a self-reported questionnaire that measures autonomic symptoms related to six domains: OI, vasomotor, secretomotor, gastrointestinal (GI), bladder and pupillomotor. This questionnaire generates a weighted score from 0 to 100, with higher scores representing higher

symptom burden. A COMPASS-31 score of ≥ 40 indicates that subjects have severe autonomic dysfunction. The OI subscale was chosen as its own key secondary endpoint as OI symptoms were found to be most prominent to differentiate between POTS and other dysautonomias, covering the most burdensome and frequent symptoms reported by POTS subjects.

Table 5: COMPASS-31

1. In the past 7 days, have you ever felt faint, dizzy, "goofy", or had difficulty thinking soon after standing up from a sitting or lying position?	Yes=1; No=0
2. When standing up, how frequently do you get these feelings or symptoms?	Rarely = 0 Occasionally = 1 Frequently = 2 Almost always = 3
3. How would you rate the severity of these feelings or symptoms?	Mild = 1 Moderate = 2 Severe = 3
4. In the past 7 days, have these feelings or symptoms that you have experienced:	Gotten much worse =3 Gotten somewhat worse = 2 Staying about the same = 1 Gotten somewhat better = 0 Gotten much better = 0 Completely gone = 0
Total Orthostatic Intolerance score	Sum(Q1 – Q4) *4
5. In the past 7 days, have you ever noticed color changes in your skin, such as red, white, or purple? (If you answer no, please skip to question 8)	Yes=1; No=0
6. What parts of your body are affected by these color changes?	Hands = 1 Feet = 1 Hands and Feet = 2
7. Have these changes in your skin color:	Getting much worse =3 Getting somewhat worse = 2 Staying about the same = 1 Getting somewhat better = 0 Getting much better = 0 Completely gone = 0
Total Vasomotor score	Sum(Q5 – Q7) *0.83333333
8. In the past 7 days, what changes, if any, have occurred in your general body sweating?	I sweat much more than I used to = 1 I sweat somewhat more than I used to = 0 I haven't noticed any changes in my sweating = 0 I sweat somewhat less than I used to = 1 I sweat much less than I used to = 2
9. Do your eyes feel excessively dry?	Yes=1; No=0
10. Does your mouth feel excessively dry?	Yes=1; No=0
11. For the symptom of dry eyes or dry mouth that you have had for the longest period of time, has this symptom:	Getting much worse =3 Getting somewhat worse = 2 Staying about the same = 1 Getting somewhat better = 0 Getting much better = 0 Completely gone = 0 I have not had any of these symptoms = 0
Total Secretomotor score	Sum(Q8 – Q11) *2.1428571

CONFIDENTIAL

12. In the past 7 days, have you noticed any changes in how quickly you get full when eating a meal?	I get full a lot more quickly now than I used to = 2 I get full more quickly now than I used to = 1 I haven't noticed any change = 0 I get full less quickly now than I used to = 0 I get full a lot less quickly now than I used to = 0
13. In the past 7 days, have you felt excessively full or persistently full (bloated feeling) after a meal?	Never = 0 Sometimes = 1 A lot of the time = 2
14. In the past 7 days, have you vomited after a meal?	Never = 0 Sometimes = 1 A lot of the time = 2
15. In the past 7 days, have you had a cramping or colicky abdominal pain?	Never = 0 Sometimes = 1 A lot of the time = 2
16. In the past 7 days, have you had any bouts of diarrhea? (If you answer no, please skip to question 20)	Yes=1; No=0
17. How frequently does this occur?	Rarely = 0 Occasionally = 1 Frequently = 2 Almost always = 3
18. How severe are these bouts of diarrhea?	Mild = 1 Moderate = 2 Severe = 3
19. Have your bouts of diarrhea gotten:	Much worse =3 Somewhat worse = 2 Stayed about the same = 1 Somewhat better = 0 Much better = 0 Completely gone = 0
20. In the past 7 days, have you been constipated? (If you answer no, please skip to question 24)	Yes=1; No=0
21. How frequently are you constipated?	Rarely = 0 Occasionally = 1 Frequently = 2 Almost always = 3
22. How severe are these episodes of constipation?	Mild = 1 Moderate = 2 Severe = 3
23. Has your constipation gotten:	Much worse =3 Somewhat worse = 2 Staying about the same = 1 Somewhat better = 0 Much better = 0 Completely gone = 0
Total Gastrointestinal score	Sum(Q12 – Q23) *0.8928571
24. In the past 7 days, have you ever lost control of your bladder function?	Never = 0 Occasionally = 1 Frequently = 2 Constantly = 3
25. In the past 7 days, have you had difficulty passing urine?	Never = 0 Occasionally = 1 Frequently = 2 Constantly = 3

CONFIDENTIAL

26. In the past 7 days, have you had trouble completely emptying your bladder?	Never = 0 Occasionally = 1 Frequently = 2 Constantly = 3
Total Bladder score	Sum(Q24 – Q26) *1.111111
27. In the past 7 days, without sunglasses or tinted glasses, has bright light bothered your eyes? (If you mark never, please skip to question 29)	Never = 0 Occasionally = 1 Frequently = 2 Constantly = 3
28. How severe is this sensitivity to bright light?	Mild = 1 Moderate = 2 Severe = 3
29. In the past 7 days, have you had trouble focusing your eyes? (If you mark never, please skip to question 31)	Never = 0 Occasionally = 1 Frequently = 2 Constantly = 3
30. How severe is this focusing problem?	Mild = 1 Moderate = 2 Severe = 3
31. Has the most troublesome symptom with your eyes (i.e. sensitivity to bright light or trouble focusing) gotten:	Much worse = 3 Somewhat worse = 2 Stayed about the same = 1 Somewhat better = 0 Much better = 0 Completely gone = 0 I have not had any of these symptoms = 0
Total Pupillomotor score	Sum(Q27 – Q31) *0.333333
Total COMPASS-31 Score	Sum (Total Orthostatic Intolerance score, Total Vasomotor score, Total Secretomotor score, Total Gastrointestinal score, Total Bladder score, Total Pupillomotor score)

Malmö Symptom Score

The Malmö Symptom score is a self-assessment of symptom burden using a visual analog scale graded from 0 (no symptoms) to 10 (very pronounced symptoms) based on 12 commonly reported symptoms: 5 cardiac symptoms (palpitations, dizziness, presyncope, dyspnea, chest pain) and 7 non-cardiac symptoms (GI, insomnia, concentration difficulties, headache, myalgia, nausea, fatigue). The scores for each symptom are summed to give a total score, which ranges from 0 to 120.

CONFIDENTIAL

Table 6: Malmö

1. Dizziness in upright position while standing up										
0	1	2	3	4	5	6	7	8	9	10
2. Dizziness, feeling you are going to faint										
0	1	2	3	4	5	6	7	8	9	10
3. Palpitations, high pulse, or feeling heart beating irregularly										
0	1	2	3	4	5	6	7	8	9	10
4. Difficult breathing/dyspnoea, both at effort and rest										
0	1	2	3	4	5	6	7	8	9	10
5. Chest pain										
0	1	2	3	4	5	6	7	8	9	10
6. Headache										
0	1	2	3	4	5	6	7	8	9	10
7. Concentration difficulties and/or problems with thinking										
0	1	2	3	4	5	6	7	8	9	10
8. Muscle pain										
0	1	2	3	4	5	6	7	8	9	10
9. Nausea										
0	1	2	3	4	5	6	7	8	9	10
10. Gastrointestinal problems										
0	1	2	3	4	5	6	7	8	9	10
11. Abnormal tiredness that persists after rest										
0	1	2	3	4	5	6	7	8	9	10
12. Insomnia										
0	1	2	3	4	5	6	7	8	9	10

Short Form – 12 Item (SF-12)

Data of the SF-12 will not be summarized but provided in the SDTM data sets.

Orthostatic Hypotension Questionnaire (OHQ)

The OHQ is a 10-item instrument developed to measure the presence and severity of symptoms and the impact of orthostatic symptoms on daily activities. It contains 2 domains: Orthostatic Hypotension Symptom Assessment (OHSA) (6 items, items 1 to 6 in [Table 7](#)) and Orthostatic

CONFIDENTIAL

Hypotension Daily Activity Scale (OHDAS) (4 items, items 7 to 10 in Table 7). Higher score indicates more severe symptoms. The instructions to the OHQ were modified to exclude the note: “*You should rate only the symptoms that are due to your low blood pressure problem* » to make them more relevant to the study population.

The OHQ composite score is the sum of the scores from both the OHSA and OHDAS components, resulting in a total score that ranges from 0 to 100.

Table 7: OHQ

	1. Dizziness, lightheadedness, feeling faint, or feeling like you black out											
none	0	1	2	3	4	5	6	7	8	9	10	Worst possible
	2. Problems with vision (blurring, seeing spots, tunnel vision, etc.)											
none	0	1	2	3	4	5	6	7	8	9	10	Worst possible
	3. Weakness											
none	0	1	2	3	4	5	6	7	8	9	10	Worst possible
	4. Fatigue											
none	0	1	2	3	4	5	6	7	8	9	10	Worst possible
	5. Trouble concentrating											
none	0	1	2	3	4	5	6	7	8	9	10	Worst possible
	6. Head and neck discomfort											
none	0	1	2	3	4	5	6	7	8	9	10	Worst possible
	7. Activities that require standing for a short time											
none	0	1	2	3	4	5	6	7	8	9	10	Worst possible
	8. Activities that require standing for a long time											
none	0	1	2	3	4	5	6	7	8	9	10	Worst possible
	9. Activities that require walking for a short time											
none	0	1	2	3	4	5	6	7	8	9	10	Worst possible
	10. Activities that require walking for a long time											
none	0	1	2	3	4	5	6	7	8	9	10	Worst possible

EuroQoL 5-Dimension Questionnaire (EQ-5D-5L)

Data of EQ-5D-5L will not be summarized but provided in the SDTM data sets.

CONFIDENTIAL

Work Productivity and Activity Impairment Questionnaire: Specific Health Problem (WPAI:SHP)

Data of WPAI:SHP will not be summarized but provided in the SDTM data sets.

Patient Global Impression of Severity (PGI-S) and Patient Global Impression of Change (PGI-C)

Table 8: PGI-S and PGI-C

Patient Global Impression of Severity (overall) Considering all the ways POTS affects you, please choose the response below that best describes the severity of your overall symptoms over the past month	None Mild Moderate Severe Very Severe
Patient Global Impression of Change (overall) Considering all the ways POTS affects you, how would you rate the change in your overall symptoms since you started taking the study medication?	Much Improved A Little Bit Improved No change A Little Bit Worse Much Worse
Patient Global Impression of Severity (Orthostatic Intolerance) Please choose the response below that best describes the severity of your discomfort when you are in the upright position over the past month	None Mild Moderate Severe Very Severe
Patient Global Impression of Change (Orthostatic Intolerance) How would you rate the change in your ability to remain upright without experiencing discomfort since you started taking the study medication?	Much Improved A Little Bit Improved No change A Little Bit Worse Much Worse

The PGI-S assesses the severity of OI and general symptoms, and the PGI-C assesses the change in severity of OI symptoms and overall disease impact. Responses to PGI-S and PGI-C for OI symptoms will be summarized by treatment group.

PROMIS Cognitive Functioning Short Form 6a

Data of PROMIS Cognitive Functioning Short Form 6a will not be summarized but provided in the SDTM data sets.

